#### Specific Aim1a:

This aim will use existing data from three prior studies [i.e., The Combined Pharmaco-therapies and Behavioral Interventions conducted in the United States (COMBINE Study)[1], a double-blind, placebo-controlled randomized trial conducted in Germany (PREDICT Study)[2], and “A Pharmacogenomic Probe Study of Acamprosate: Genes Associated with Response” Mayo Clinic Center for the Individualized Treatment of Alcohol

study (CITA); total N=1687], to assess the heritability explained by common single nucleotide polymorphisms (SNPs) and the genetic architecture for different measures of alcoholism treatment response. We will use this data to estimate the heritability of different outcomes in patients treated with acamprosate, placebo and naltrexone (as active drug control) that can be explained by common SNPs. We will also investigate the sources of genetic contribution to different treatment outcomes in terms of the distribution of the genetic signal across minor allele frequencies and functional annotation categories. These analyses may help determine if sobriety or another treatment outcome (e.g. return to heavy drinking) is the most suitable phenotype for subsequent pharmacogenomic analyses of acamprosate treatment response.

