#### Specific Aim 2a:

We will conduct a genome-wide association study (GWAS) in the newly enrolled sample of 800 alcoholic patients. Using acamprosate and placebo arms in the new study cohort will allow identification of genetic markers associated with acamprosate-specific effects impacting treatment outcomes, including sobriety (primary outcome) and other outcomes selected based on the results of Aim 1a. We will also conduct a meta-analysis including existing data from aim 1, which will be the largest pharmacogenomic study of AUD treatment outcomes to date (total N > 2400).

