#### Analysis for Specific Aim 2a

Genetic association analyses will evaluate the effect of SNP genotypes on acamprosate and placebo treatment outcomes. Well-established pipelines will be used for genotype quality control and imputation prior to performing the genetic association analyses. We will first perform genome-wide association analyses of the primary outcomes in the acamprosate-treated participants with available 3 month outcomes, using standard approaches. For example, we will evaluate the association of SNPs with 3 month continuous abstinence (yes/no) using logistic regression and with length of abstinence using Cox proportional hazard models. We will first use these models to evaluate the association of the treatment outcomes with covariates, including demographic and baseline clinical characteristics, such as depression and anxiety symptom severity (PHQ-9 and GAD-7 scores, respectively), and liver function tests (LFTs) – aspartate aminotransferase (AST), alanine transaminase (ALT) and Gamma-Glutamyltransferase (GGT). SNP association with the primary treatment outcomes will be evaluated while adjusting for relevant covariates and principal components derived from genome-wide SNP data to adjust for population stratification. As discussed in the Statistics Team Section, secondary analyses will also be performed using the entire sample of participants enrolled into the study [“intent-to-treat” (ITT) analysis]. If the same genetic variants contribute to lack of response in the “completer” group and to early dropout (which is likely the case as early dropout frequently results from relapse), the ITT analysis will have greater power than the “completer” analysis. We will also perform genome-wide association analyses using all participants (acamprosate and placebo), including a treatment covariate, and a SNP-treatment interaction to evaluate whether SNPs are associated with clinical outcomes in a drug-dependent manner (e.g. SNP is associated with acamprosate treatment outcome, but not placebo treatment outcome). We will

also evaluate the possibility of sex-specific genetic effects, or genetic effects that are modified by the presence of comorbidities such as depression and anxiety, by exploratory analyses involving interaction terms with these variables.

Most importantly, we will perform a genome-wide meta-analysis of acamprosate pharmacogenomics using the new data and data from available prior studies (COMBINE, PREDICT, CITA; see Aim 1).

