As with the analysis described above, our meta-analyses will also include analyses of the full set of acamprosate and placebo treated participants, with a treatment covariate and tests of SNP-treatment interaction effects. However, our power estimate for the meta-analysis is based only on the combined sample of acamprosate-treated patients, since the size of this sample will determine the power to detect acamprosate-specific pharmacogenomics effects. Assuming a total sample of 1000 acamprosate-treated participants (ITT), the meta-analysis will provide 80% power to detect associations of SNPs with 3-month abstinence during acamprosate treatment (assume ~1/3 abstain and 2/3 relapse) with odds ratios of 2.07 and 1.80 for SNPs with minor allele frequencies (MAFs) of 0.2 and 0.4, respectively, at a genome-wide significance level of  $5 \times 10^{-8}$ . We also note that analyses of the full dataset (N≈1500) including participants that received acamprosate or other treatment options will provide greater power to detect genetic predictors of treatment-independent predictors of abstinence in patients with AUD.

We recognize that the available sample has relatively little power to detect the effects of individual SNPs, which tend to be very modest for complex traits such as alcohol-dependence related phenotypes. We will therefore apply more advanced analysis methods to maximize power of the study, including gene-level and pathway-based (gene-set) analyses using approaches such as MAGMA [42], and will evaluate polygenic risk score associations and AUD treatment outcomes.

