### ***Limitations and Proposed solutions***

- The proposed study design may not allow for the separation of the effects of depression and anxiety from the treatment effects of SSRIs, and SNRIs listed on an association between genetic variation and acamprosate or placebo-related treatment outcomes. Separation of those effects would have required an additional placebo arm for antidepressant treatment. We considered this option but concluded it would not be feasible and may negatively affect the attainment of the primary study goal - i.e. identification of genetic markers associated with acamprosate-related treatment outcomes in participants with AUD. Therefore, the difference between the effects related to presence/severity of depression or anxiety and the effects of antidepressant treatment on an association between genetic variation and acamprosate or placebo-related treatment outcomes will need to be investigated in future studies.
- Although the size of the new study sample proposed for the pharmacogenomic analyses in Aim 2 is comparable or exceeds the size of samples collected for the CITA, COMBINE and PREDICTS studies, this sample alone is still unlikely to provide sufficient power to detect significant associations. However, as described above, our goal is to conduct a meta-analysis to identify pharmacogenomic markers associated with response to acamprosate in a combined sample including participants enrolled as part of the proposed center as well as those collected in the COMBINE, PREDICT and CITA studies. This will be the largest pharmacogenomics GWAS in AUD to date. Moreover, the sample will also include a large set of placebo-treated participants ( $N \approx 800$ ) allowing for differentiation between acamprosate-specific pharmacogenomic effects from treatment independent predictors of abstinence in patients with AUDs.

We also expect that the application of pharmacometabolomics- and imaging-guided pharmacogenetic analyses of the acamprosate-related outcomes described in Aim 3 will allow for the use of intermediate phenotypes (namely metabolomic and neuro-imaging signatures associated with acamprosate response) and will improve the power for the discovery of genetic variations predictive of response to acamprosate.

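### The reason for powering on acamprosate patients alone does not hold for the planned SNP-treatment interaction, whose power is not given and depends on the placebo arm at least as much

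*Combined protocol and SAP*

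**What the plan says.** Analysis for Specific Aim 2a first plans a scan in acamprosate-treated patients. It then plans "genome-wide association analyses using all participants (acamprosate and placebo), including a treatment covariate, and a SNP-treatment interaction", to find SNPs that act in one arm and not the other. The meta-analysis is to repeat this on the "full set of acamprosate and placebo treated participants, with a treatment covariate and tests of SNP-treatment interaction effects".

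The next sentence turns away from the interaction and bases power on acamprosate-treated patients only, "since the size of this sample will determine the power to detect acamprosate-specific pharmacogenomics effects". With 1000 such patients, about 1/3 of them abstinent, the plan claims "80% power to detect associations of SNPs with 3-month abstinence during acamprosate treatment" for odds ratios of 2.07 (MAF 0.2) and 1.80 (MAF 0.4) at 5e-8. No power, detectable effect or significance level is given for the interaction.

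Elsewhere the placebo patients carry the drug-specific question. The opening statement of Specific Aim 2a says: "Using acamprosate and placebo arms in the new study cohort will allow identification of genetic markers associated with acamprosate-specific effects". Limitations and Proposed solutions cites about 800 placebo-treated participants as "allowing for differentiation between acamprosate-specific pharmacogenomic effects from treatment independent predictors of abstinence".

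**The concern.** An association seen in acamprosate patients alone may be a predictor of abstinence under any treatment. The protocol's Purpose/Background makes this point about the earlier study, which had no placebo arm. Drug specificity is a contrast between arms, and the precision of a contrast depends on both. A clause saying that one arm's size settles the power for drug-specific effects invites the reader to carry the 80% over to the interaction. This is the plan's only numerical power statement, and the drug-specific question is the declared reason for having two arms. The fault is an over-broad justification and a missing figure, not a slip in arithmetic.

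**Working it through.** **Inputs from the plan.** 1000 acamprosate patients, 1/3 abstinent, OR 2.07 at MAF 0.2 and OR 1.80 at MAF 0.4, 5e-8 (Analysis for Specific Aim 2a); about 800 placebo patients (Limitations and Proposed solutions).

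**Assumptions, because the plan gives none for the interaction.** Per-allele coding, Hardy-Weinberg genotypes, two-sided 5e-8 (critical value 5.451), 1/3 abstinent on placebo, and placebo OR 1. The last is the plan's own example of a drug-dependent SNP, so the interaction OR equals the acamprosate OR.

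**Step 1: the plan's own figure.** Let I be the per-patient logistic information for the SNP, with the intercept set to give 1/3 abstinent overall. On acamprosate, I = 0.07198 (MAF 0.2) and 0.10162 (MAF 0.4). Power = Φ(ln OR × √(1000 × I) − 5.451).
- MAF 0.2: Φ(0.7275/0.1179 − 5.451) = 76%. Likelihood-ratio and score versions give 78% and about 80%.
- MAF 0.4: Φ(0.5878/0.0992 − 5.451) = 68%. The other two versions give 71%.

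The 80% is close at MAF 0.2 and not reached at MAF 0.4. A 50:50 outcome split gives 80.5% and 80.3% (likelihood ratio).

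**Step 2: the interaction.** Variance = 1/(N_acamprosate × I_acamprosate) + 1/(N_placebo × I_placebo). With OR 1 on placebo, I_placebo = (1/3)(2/3) × 2 × MAF × (1 − MAF) = 0.07111 and 0.10667.

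| | MAF 0.2, OR 2.07 | MAF 0.4, OR 1.80 |
|---|---|---|
| Acamprosate term, N = 1000 | 0.01389 | 0.00984 |
| Placebo term, N = 800 | 0.01758 | 0.01172 |
| Placebo share of variance | 55.9% | 54.4% |
| Standard error | 0.1774 | 0.1468 |
| ln OR / SE | 4.10 | 4.00 |
| Power, Φ(ratio − 5.451) | 8.8% | 7.4% |
| Interaction OR for 80% power | 3.13 | 2.58 |

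Simulation with Wald tests (20,000 replicates) gave 8.0% and 7.0%.

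**Step 3: which sample limits power.** With 800 placebo and unlimited acamprosate patients, power stops at 51%/49%. With 1000 acamprosate and unlimited placebo patients, it stops at 76%/68%, the within-acamprosate value. Each arm sets a ceiling; neither determines power alone.

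**Step 4: how far the result moves** (MAF 0.2/0.4; 1000/800, 5e-8 and 1/3 on placebo unless stated).
- Placebo abstinence 20%: 4.2%/3.5%. At 45%: 11.0%/9.1%. Table 2's whole-study rates run from 21.2% to 45.5%.
- Larger counts. Table 2 has 608 + 172 + 443 = 1223 acamprosate and 466 + 85 = 551 without active drug. Adding the new 800 split 1:1 gives 1623/951 and power 24.5%/21.4%; split 2:1 it gives 1756/818 and 19.5%/17.1%. These counts are generous, since the COMBINE arms overlap through co-treatment. Adding 45% placebo abstinence to 1623/951 gives 30%/26%.
- Odds ratios rescaled so that the within-acamprosate test has exactly 80%: about 10-12%.
- Placebo OR of 1.2 in the same direction: under 1%. Opposite direction (1/1.2): 35%/41%.
- Interaction threshold 1e-5: 38%/34%. At 1e-4: 58%/55%. At 0.05: 98%/98%.

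**The case against.** The strongest reply is that the interaction need not be a discovery test. The plan runs the acamprosate scan first and gives the placebo patients a differentiating role. If only SNPs passing that scan were tested for interaction at 0.05, interaction power would be about 98% and joint power 76%/68%, the same as for the scan alone. The acamprosate sample would then be the limiting one and the clause nearly right. This stands as a possible design. The plan does not describe it: the interaction sits inside the genome-wide analyses of all participants, with no selection step and no threshold of its own.

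The plan also words its 80% as association during acamprosate treatment, and it concedes little power for individual SNPs before turning to gene-set and polygenic methods. Both are fair. The concession is general, though. It neither withdraws the clause nor says that the drug-specific test is much weaker than the one quoted.

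Three stronger readings should be resisted.
- A reader might take 1500 − 1000 = 500 as the placebo number and arrive at 2-3% power. The source is "analyses of the full dataset (N≈1500) including participants that received acamprosate or other treatment options", so the remainder is not stated to be placebo. The plan's placebo figure is about 800, and 551 + 267 (one third of 800) = 818 agrees with it.
- A reader might conclude that the drug-specific analysis definitely has single-digit power. That rests on an assumed 5e-8 and an assumed null effect on placebo.
- A reader might call the 80% wrong. The plan does not give the test version or say which rate the 1/3 describes. If 1/3 is the reference-genotype rate, the result is 79%/76%. This calls for a recheck; it does not establish an error.

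**Conclusion.** The point holds in limited form and should be fixed. The stated reason is valid for SNP association within acamprosate patients and fails for the interaction as the plan describes it. At 1000/800 the placebo arm contributes 54-56% of the interaction variance. Power at the quoted odds ratios is about 7-9% under the assumptions above, 3-11% if placebo abstinence is 20-45%, and up to about 25% with the larger counts at 1/3 abstinent on placebo. At 5e-8, no combination of sample size, placebo abstinence and placebo effect tried comes near 80%. The size of the shortfall depends on a threshold and role that the plan leaves unstated; the failure of the reason for a genome-wide interaction does not depend on the exact figures.

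**What to change.** 1. Replace the clause with a statement that the quoted power applies to SNP association within acamprosate-treated patients only. Recheck that figure and state the test and outcome split behind it, since at 1/3 abstinent it recomputes to about 76-80% (MAF 0.2) and 68-71% (MAF 0.4).
2. State whether the interaction is a genome-wide scan or a follow-up of SNPs passing the acamprosate scan, and give its significance threshold.
3. Report the interaction odds ratio detectable with 80% power at that threshold and at the placebo number the meta-analysis will use. At 5e-8 with 1000/800 it is about 3.1 (MAF 0.2) and 2.6 (MAF 0.4).

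The cost is some wording and one recalculation. The stated position on the drug-specific question becomes less favourable. No patients or procedures are added.

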To identify metabolomic markers associated with length of sobriety and other acamprosate related clinical outcomes in 800 patients with AUD recruited to a new trial in which the patients will be randomized to acamprosate or placebo using the same two metabolomic platforms used in Aim 1b in order to replicate and extend results found during the earlier non-placebo controlled study of 445 AUD patients and to identify new candidate metabolites. We will then apply a “pharmacometabolomics-informed pharmacogenomics” research strategy to pursue the metabolites found to be associated with drug response outcomes during the placebo-controlled study.

Using acamprosate and placebo arms in the new study cohort will allow identification of genetic markers associated with acamprosate-specific effects impacting treatment outcomes, including sobriety (primary outcome) and other outcomes selected based on the results of Aim 1. We will also conduct a meta-analysis of

pharmacogenomic effects on acamprosate response, which will be the largest pharmacogenomic study of AUD treatment outcomes to date (total N > 2000).

To accomplish Aims 2a and 2b, 800 patients meeting Diagnostic and Statistical Manual of Mental Disorders, Fifth Edition (DSM5) criteria for AUD will be recruited from community-based treatment programs affiliated with Mayo Clinic and Mayo Health System and Hazelden Betty Ford Foundation and enrolled in a double-blind randomized placebo-controlled trial of acamprosate (Fig. 1).

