Table 2 Subject Characteristics	COMBINE	PREDICT	CITA
N	1393	426	443
Age, mean(SD)	44.4 (10.2)	45.3 (8.7)	42.1 (11.8)
Sex, N(%) male	955 (69%)	328 (77%)	286 (65%)
Race, N(%) white non-Hispanic	1062 (77%)	426 (100%)	412 (93%)
Baseline Consumption Measures (last 30 days)			
Average drinks per drinking day	13.0 (8.1)	19.4 (11.3)	11.8 (7.7)
% drinking days	72.8 (23.5)	82.1 (1.3)	50.7 (29.7)
% heavy drinking days	65.2 (24.9)	79.0 (1.3)	45.8 (29.7)
Number of days since last drink	7.7 (5.3)	22.1 (4.4)	24.8 (16.1)
Medications			
Acamprosate, N	608	172	443
Naltrexone, N	614	169	0
No active drug (placebo or no medication), N	466	85	0
Treatment outcomes			
3 month abstinence from any drinking, N(%)	293 (21.2)	194 (45.5)	132 (29.7)
3 month abstinence from heavy drinking, N(%)	432 (31.2)	210 (49.3)	168 (37.9)

For COMBINE and CITA, baseline consumption is based on 30 days prior to the start of medication, while for PREDICT it is based on 30 days prior to the onset of inpatient treatment, as proposed by Mann and colleagues (84).

For the COMBINE study, the number of participants for each medication may include participants on more than one medication (i.e. groups are not mutually exclusive since the study included acamprosate/naltrexone co-treatment).

Numbers for treatment outcomes are based on the ITT sample (i.e. complete sample) assuming those who dropped out prior to 3 months had returned to heavy drinking.

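### Meta-analysis power: at the stated one-third abstinence, an odds ratio of 1.80 at MAF 0.4 has about 71% power, not 80%, unless one-third means something else; and a full dataset of about 1500 conflicts with the plan's other totals (minor)

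*Combined protocol and SAP*

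**What the plan says.** The power statement is in the Combined protocol and SAP, Analysis for Specific Aim 2a, after Table 2. Its inputs are:

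- Sample: "Assuming a total sample of 1000 acamprosate-treated participants (ITT").
- Outcome split: "assume ~1/3 abstain and 2/3 relapse".
- Significance level: 5×10⁻⁸. Claimed power: 80%.
- Detectable effects: "odds ratios of 2.07 and 1.80 for SNPs with minor allele frequencies (MAFs) of 0.2 and 0.4".

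Earlier in the same section the test for this outcome is named: "we will evaluate the association of SNPs with 3 month continuous abstinence (yes/no) using logistic regression". The genotype coding, the sidedness, and whether one-third is the rate in the whole sample or in the reference genotype are not stated.

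The power paragraph then refers to "analyses of the full dataset (N≈1500) including participants that received acamprosate or other treatment options". Other sections give different sizes for the combined data. Research Design describes the meta-analysis as one "which will be the largest pharmacogenomic study of AUD treatment outcomes to date (total N > 2000"). Specific Aim 2a and Purpose/Background both give more than 2400.

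**The concern.** This is the only power figure for the meta-analysis, which the plan treats as its main genetic analysis. Limitations and Proposed solutions relies on that meta-analysis because the new sample alone is not expected to be large enough. A reader who enters the printed inputs into the printed test recovers one of the two odds ratios but not the other.

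At the stated inputs, a SNP with MAF 0.4 and odds ratio 1.80 would be missed about 29% of the time instead of 20%. The dataset size in the next sentence is also too small for a combined sample that includes the new trial.

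**Working it through.** **Inputs from the plan:** N = 1000, α = 5×10⁻⁸, abstinence 1/3, odds ratios 2.07 (MAF 0.2) and 1.80 (MAF 0.4), logistic regression.

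**Assumed, because not stated:** log-additive coding (0, 1, 2 minor alleles), Hardy-Weinberg proportions, two-sided test, minor allele favouring abstinence.

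**Method.** With MAF q, the genotype frequencies g are (1−q)², 2q(1−q) and q². Abstinence in genotype x is p(x) = 1/(1+exp(−(b + x·ln OR))), with b chosen so that Σg·p equals the overall rate K. The non-centrality of the 1-df likelihood-ratio test is λ = 2N(L1 − L0), where L1 = Σg[p ln p + (1−p) ln(1−p)] and L0 = K ln K + (1−K) ln(1−K). The critical value at 5×10⁻⁸ is 29.72, and 80% power needs λ = 39.60.

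**Step 1: one-third as the overall rate** (L0 = −0.636514)

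| | MAF 0.2, OR 2.07 | MAF 0.4, OR 1.80 |
|---|---|---|
| Genotype frequencies | 0.64, 0.32, 0.04 | 0.36, 0.48, 0.16 |
| Abstinence by genotype | 0.268, 0.431, 0.610 | 0.233, 0.354, 0.497 |
| L1 | −0.617117 | −0.618409 |
| λ | 38.79 | 36.21 |
| Power | 78.2% | **71.4%** |
| 80%-power OR | 2.09 | **1.85** |

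The plan's MAF 0.2 figure is reproduced within rounding; the MAF 0.4 figure is not. The N for 80% at MAF 0.4 is 1000 × 39.60/36.21 ≈ 1094. Other forms of the two-sided logistic test agree at MAF 0.4: score 71.2%, Wald 68.2%, simulated likelihood-ratio 71–72%.

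**Step 2: one-third as the reference-genotype rate** (odds 0.5 in non-carriers)

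- MAF 0.2: genotype rates 0.333, 0.509, 0.682; λ = 40.40; power 81.7%. Overall abstinence is 0.64×0.333 + 0.32×0.509 + 0.04×0.682 = 40.3%.
- MAF 0.4: genotype rates 0.333, 0.474, 0.618; λ = 39.59; power 80.0%. Overall abstinence is 0.36×0.333 + 0.48×0.474 + 0.16×0.618 = 44.6%.

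Both figures are recovered, but only with 40–45% abstinent.

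**Step 3: varying the overall rate** (N = 1000, two-sided)

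| Overall abstinence | OR 2.07, MAF 0.2 | OR 1.80, MAF 0.4 |
|---|---|---|
| 27.4% | 70.6% | 60.5% |
| 33.3% | 78.2% | 71.4% |
| 35% | 79.4% | 73.6% |
| 40% | 81.6% | 78.0% |
| 45% | 81.9% | 80.1% |
| 50% | 80.5% | 80.3% |

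The 27.4% is Table 2 pooled over all arms: (293 + 194 + 132)/(1393 + 426 + 443) = 619/2262. On the basis of these counts Table 2 says: "Numbers for treatment outcomes are based on the ITT sample (i.e. complete sample"), with dropouts counted as having returned to heavy drinking.

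**Step 4: the assumed N.** Table 2 lists 608 + 172 + 443 = 1223 acamprosate-treated participants before the new trial. At N = 1223 and one-third overall, power for OR 1.80 at MAF 0.4 is 88.6%. The plan does not say how 1000 was reached.

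**Step 5: dataset size**

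| Source in the plan | Combined size |
|---|---|
| Analysis for Specific Aim 2a, full dataset | about 1500 |
| Research Design | > 2000 |
| Specific Aim 2a; Purpose/Background | > 2400 |
| Specific Aim 1a (1687) + new trial (800) | 2487 |
| 1000 acamprosate + about 800 placebo (Limitations and Proposed solutions) | about 1800, before naltrexone-only patients |

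Only the Introduction's count of roughly 1,500 patients in the completed studies matches, and that excludes the new trial.

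**The case against.** The strongest reply is that the plan leaves open which rate one-third describes. With one-third as the reference-genotype rate, the same two-sided model gives 81.7% and 80.0%, so 80% cannot be called unattainable. This stands, and the point is conditional for that reason. It does not rescue the sentence as printed: two-thirds relapsing describes the whole sample, and this reading gives a single cohort two different overall rates, both further from Table 2's 27.4%.

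Other test choices also come closer. One-sided logistic tests give 73–76% at MAF 0.4. One-sided allelic tests give 78–81% there, and one version gives 78% at both frequencies. An allelic test is not the logistic regression that the plan names.

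The assumed 1000 may be conservative given the 1223 in Table 2, which would raise power. The lower abstinence in Table 2 would reduce it. The number usable for the genetic analysis is not given: Table 2 totals 2262 against 1687 in Specific Aim 1a. So 71% describes the printed inputs and is not a forecast for the study.

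The plan also warns that "the available sample has relatively little power to detect the effects of individual SNPs" and turns to gene-level, pathway and polygenic analyses. A reader is not led to expect strong single-SNP power. This is why the point is minor.

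The conflict over 1500 has no comparable defence, but that figure has no power calculation attached to it.

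**Conclusion.** Wrong as written, and minor. With one-third as the overall abstinence rate, N = 1000, and a two-sided log-additive logistic test, the claim for MAF 0.2 holds (78%, 80%-power OR about 2.09). The claim for MAF 0.4 does not (about 71%, 80%-power OR about 1.85). With that test, both printed odds ratios are near 80% only when overall abstinence is about 40–50%, which includes the reference-genotype reading. That fits neither the stated split nor Table 2.

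The full dataset of about 1500 cannot be the combined sample described elsewhere in the plan.

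Three stronger inferences are not supported:

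- That the odds ratios were computed at a 50:50 split. That split gives 80%-power odds ratios of 2.07 and 1.80 to two decimals, but the reference-genotype reading gives 2.05 and 1.80. The documents do not show how the figures were obtained.
- That the trial is too small. The target of 800 is not derived from this calculation.
- That more than 2000 and more than 2400 contradict each other. Both are lower bounds, and 2487 satisfies both.

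**What to change.** In Analysis for Specific Aim 2a:

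1. State the genotype coding, the sidedness, and whether one-third is the overall or the reference-genotype abstinence rate.
2. If one-third overall and N = 1000 are kept, print odds ratios of about 2.09 and 1.85, or keep the printed ones and give power of about 78% and 71%. Otherwise state the abstinence rate that yields 2.07 and 1.80, and reconcile it with Table 2.
3. State how the 1000 was reached, given the 1223 in Table 2.
4. Replace the 1500 with the combined total, or name the subset it describes, so that it agrees with the other sections.

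The cost is one recalculation and a few sentences. No patients are added, and no test or significance threshold changes.
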